12.6.4.1 Safety Reporting

An exposure emergent AE is defined as an AE that occurs after first product use or that is present prior to first product use and becomes more severe after first product use. All other AEs will not be summarized but provided in listings only.

All AEs occurring from the time of signing of informed consent will be recorded electronically. However, during the screening period (prior to first product use), only study related AEs will be summarized. The AE listings will include all AEs captured in the database at any time during the study (including those from subjects who were not in the Safety Population).

AEs reported from subjects that have a first product use, but were not randomized will be summarized in a separate group: “Exposed but not randomized”.

Partial dates will not be imputed, but assumptions will be made as follows to assign to product-emergent or not:

Date information	Assign as
Partial date, e.g. --May2012, or ----2011. If month/year is the same as, or later than the month and/or year of Screening.	Product-emergent
Partial date, e.g. --May2012, or ----2011. If month and/or year is earlier than the month and/or year of Screening.	Not product-emergent

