8.2.1 Collection of Information

Adverse event information will be collected from the time of signature of the ICF/information sheet onwards until EOS either by the Investigator or designee via spontaneous reporting or by the use of consistent, open, non-directive questions from study site staff (e.g., “Have you had any health problems since the previous visit/How are you feeling since you were last asked?”). At the discretion of the Investigator or designee, the collection of AE information may also be triggered from his/her review of the subject questionnaires and the VAS. However, the main source for AE collection will be face-to-face interview(s) with the subject.

Information recorded will include: verbatim description of the AE, start and stop dates and times, seriousness, severity (intensity), action taken (e.g., whether or not the AE led to the subject’s withdrawal from the study), and outcome (e.g., resolved, withdrawal due to AE).

For each AE, the intensity will be graded on a 3-point intensity scale (mild, moderate, severe) using the definitions provided in Section 8.2.5.

Any exacerbation/worsening or increased frequency of an AE or pre-existing condition shall be evaluated and recorded.

Correct medical terminology/concepts are preferred when recording AE terms, and abbreviations must be avoided. Wherever possible, a diagnosis is to be used to describe an AE rather than individual signs and symptoms (e.g., record ‘pneumonia’ rather than ‘fever’, ‘cough’, ‘pulmonary infiltrate’ or ‘septicemia’ rather than ‘fever’ and ‘hypotension’ following blood sample).

Any AE that meets the serious criteria must be recorded both on the AE report form of the eCRF and on a separate SAE report form (see Section 8.3).

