8.5 Reporting and Follow-Up of Pregnancies

For pregnancies detected during the Screening period and prior to first THS 2.2 use, the subject will be considered as a screening failure and removed from the study. No Pregnancy Form will be completed, however, the diagnosed pregnancy must be captured in the Screen Failure eCRF.

All pregnancies occurring after signature of the ICF/subject information sheet and diagnosed after first exposure to the IP until completion of the study must be reported by the Investigator or designee.

Any pregnancy potentially associated to exposure to the IP, including pregnancies spontaneously reported to the Investigator or designee after the EOS must be reported by the Investigator or designee and followed-up. Potential association with exposure to the IP is defined as the conception date being calculated before the last exposure to the IP.

The Investigator or designee will complete a Pregnancy Form (provided as a separate document) for all pregnancies diagnosed (including positive urine pregnancy tests).

The procedure to report a pregnancy and provide any additional/follow-up information to [REDACTED] and the Sponsor must be followed in the same manner and within the same timelines as described for an SAE (see Section 8.3). In addition, each pregnancy has to be reported as a non-serious AE. No invasive procedures, including drawing of blood, must be done in such subjects after the discovery of pregnancy.

[REDACTED] will follow-up pregnancies only if they were detected after first product use (i.e., after THS 2.2 product test on Admission Day). If pregnancies are to be followed-up, they will be followed-up until an outcome is reached (e.g., normal delivery, spontaneous abortion, or voluntary termination). Any pregnancy complications, adverse pregnancy outcomes, or maternal complications will be recorded.

The Investigator or designee is responsible for informing the IEC of any pregnancy that occurs during the study and its outcome, according to local regulations.

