6 INVESTIGATIONAL PLAN

6.1 Study Design

This is a randomized, controlled, open-label, 3-arm parallel group, single-center study, stratified randomization by sex and average daily CC consumption over the last 4 weeks as reported during the Screening Visit (10 - 19 CC/day vs. >19 CC/day). (**Figure 1** “Study Flowchart”).

In total, 160 eligible, healthy smoking subjects will be randomized into one of the three study arms in **Table 1 “Definition of Study Arms”**.

Table 1 Definition of Study Arms

Study arm	Number of subjects
THS 2.2	80
CC	40
Smoking abstinence	40

This is an *ad libitum* smoking study. In general, smoking during confinement will be allowed between 06:30 AM and 11:00 PM.

The Screening Visit will be conducted within 4 weeks prior to Admission to the investigational site (Day -30 to Day -3). Screening procedures do not necessarily have to be conducted on the same day. During the Screening Visit the site staff will demonstrate the use of THS 2.2.

Subjects will be admitted to the clinical site on Day -2 (Admission). At Admission, in female subjects, the urine pregnancy test must be negative before the product test of THS 2.2 is performed. The THS 2.2 product test, (use of up to 3 THS Tobacco Sticks) is the last procedure of the eligibility assessments, prior to enrolment. After the inclusion and

exclusion criteria have been satisfactorily met, only subjects willing and able to use THS 2.2 will be enrolled in the study, to minimize the drop-out rate during the course of the study.

Subjects are enrolled on Day -2, and then randomized on Day 0. From Day-2 to Day 0, all subjects will continue smoking their single preferred brand of CC and baseline values will be recorded on Day -1 and Day 0. On Day 0, subjects will be randomized to 1 of the 3 study arms (see **Table 1 “Definition of Study Arms”**). Subjects will be informed of their randomized study arm by the study site staff on Day 1 prior to 06:30 AM.

[figure not shown]
The exposure period (from Day 1, 06:30 AM to Day 5, 11:00 PM) will consist of 5 days of *ad libitum* use of the assigned product between 06:30 AM and 11:00 PM each day (THS 2.2 and CC arms). Use of any tobacco/nicotine containing product other than the assigned product will not be allowed and may, at the discretion of the Principal Investigator (PI) or designee, result in the subject's withdrawal from the study.

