10.3 Safety Population

The Safety Population consists of all the subjects who had at least one exposure to THS 2.2 (product test at Admission Day). Subjects in the Safety Population will be analyzed according to actual exposure.

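### SAP 12.6.4.1 defines emergent adverse events by first product use, but its partial-date table classifies them by the Screening month

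*SAP*

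**What the plan says.** SAP 12.6.4.1 sets the reference point in its first sentence: "An exposure emergent AE is defined as an AE that occurs after first product use". It adds AEs already present that become more severe after first use. Other AEs are listed and not tabulated. The section then says that in the screening period, before first product use, only study-related AEs are summarized.

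The partial-date table in the same section has two rows. The product-emergent row applies "If month/year is the same as, or later than the month and/or year of Screening". The not-product-emergent row applies "If month and/or year is earlier than the month and/or year of Screening". The table does not say whether the date is the onset or the stop date, and it has no row for a completely missing date.

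Protocol 8.5 identifies first product use: "i.e., after THS 2.2 product test on Admission Day". SAP 10.3 uses the same product test to define the Safety Population. Protocol 8.2.1 fixes when AEs start to be recorded: "Adverse event information will be collected from the time of signature of the ICF/information sheet onwards until EOS".

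**The concern.** Screening always precedes first product use, so the table's cut-point lies earlier than the one in the definition. AEs are recorded from consent. If Screening is dated by consent, a new AE cannot carry a month before Screening, and the not-product-emergent row can be reached only by conditions that began before the study. For AEs arising in the screening period, the table therefore does not separate those before first use from those after it.

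At stake is whether some events known to precede any THS 2.2 use are counted in the emergent AE tables, including those by severity and by relationship. The SAP's own definition would put those unrelated to the study in the listings only.

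**Working it through.** The plan states no figure to reproduce. The check sets the rule against the definition and then asks when the two must disagree.

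**1. Reference dates.** Screening is Day -30 to Day -3, and admission with the product test is Day -2 (SAP 6.1). The gap g therefore runs from -2 - (-3) = 1 day to -2 - (-30) = 28 days. The day numbering can be checked against Protocol 4.4. Counting Day 0, Day -30 to Day 13 is 13 + 30 + 1 = 44 days, and Day -3 to Day 13 is 13 + 3 + 1 = 17 days. Both match the stated 17 to 44 days.

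**2. Worked example.** Take Screening on 12 August 2013, Day -2 on 9 September 2013 (g = 28), and an AE dated only to August 2013.
- SAP table: August is the Screening month, so the AE is product-emergent.
- SAP definition: all of August precedes 9 September, so the AE is not emergent unless it later worsened.

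The known month settles the order, so no imputation is needed.

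**3. When a certain conflict is possible.** Screening and Day -2 must fall in different calendar months. Assume Day -2 is spread evenly over a 365-day year. No gap exceeds 28 days, so none is longer than the shortest month. In each of the 12 months, exactly g dates of Day -2 then have Screening in the month before. The share is 12g/365. For year-only dates it is g/365.

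| Gap g (days) | Earlier month, 12g/365 | Earlier year, g/365 |
|---|---|---|
| 1 | 3.3% | 0.3% |
| 7 | 23.0% | 1.9% |
| 14 | 46.0% | 3.8% |
| 21 | 69.0% | 5.8% |
| 28 | 92.1% | 7.7% |
| Uniform over 1 to 28 (mean 14.5) | 47.7% | 4.0% |

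The gap distribution is an assumption, as the documents do not give one. These are shares of subjects in whom the conflict can arise.

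**4. Enumeration.** There are 28 gaps x 365 dates of Day -2 = 10,220 pairs. Screening is in an earlier month in 12 x (1 + 2 + ... + 28) = 12 x 406 = 4,872 of them, or 47.7%. Now pair each with an AE dated to the Screening month or to the month of Day -2. This gives 10,220 + 4,872 = 15,092 distinct combinations. Under the SAP table, 4,872 of them carry a month that ends before first use and are still called emergent. With the month of first use as comparator the number is 0, and no month that could contain a date on or after first use is lost. This tests dates only; worsening needs its own rule.

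**5. Which AEs are left.** Three conditions must all hold: the AE has a partial date, it arose in the screening period, and it is unrelated to the study. Study-related screening AEs are summarized in any case.

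**The case against.** The case on the other side has four parts.

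- **The section contains its own safeguard.** An AE dated to a month that ends before Day -2 lies in the screening period, where only study-related AEs are to be summarized. Protocol 8.2.3 similarly limits which screening AEs are carried forward for reporting. A reader might infer from the table that the emergent tables are certain to be wrong. The documents do not support that, because two instructions compete and neither is given priority. The inconsistency stands, since a programmer who follows the table gets a different result from one who follows the sentence above it.
- **The rule is conservative.** It can over-count emergent AEs but cannot miss one that starts after first use. SAP 12.6.4.2.1 takes the worst case elsewhere, counting a missing intensity as severe. This is a good answer when Screening and Day -2 share a month, because the date is then ambiguous. It does not cover a month known to end before first use, where no doubt remains to be resolved.
- **Few AEs can be affected.** Protocol 8.2.1 asks for start and stop dates and times, and Protocol 11.2.1 requires queries for missing data. This stands.
- **The arms are treated alike.** The affected events precede randomization on Day 0, and SAP 12.6.4.2.1 presents AE tables by randomized arm. This also stands: the extra counts add noise but no systematic difference between arms.

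The date wording matches SAP 12.3.3 (medical history) and 12.6.4.5.1 (prior medication), where Screening is the defining cut-point. A reader might infer that it was carried over by mistake. The documents do not say so. SAP section 9 mentions no different cut-point for AEs.

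**Conclusion.** The point holds as an inconsistency within SAP 12.6.4.1. Where Screening falls in an earlier calendar month than Day -2, or an earlier year for year-only dates, the partial-date table gives a label that the section's own definition rules out, unless the AE later worsened.

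Under the even-calendar and uniform-gap assumptions this can happen in about 48% of subjects, from 3% at a 1-day gap to 92% at 28 days. A reader might take 48% as the share of AEs misclassified, or conclude that every partially dated screening AE is misclassified. Neither follows. The figure counts subjects at risk of the conflict, and an AE dated to the admission month is ambiguous rather than wrong.

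The number of AEs is not given and is probably small. The consequence is minor: a possible over-count of emergent AEs that does not systematically bias the comparison between arms.

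**What to change.** In both rows of the partial-date table in SAP 12.6.4.1, replace Screening by first product use (Day -2 product test), and state that the rule applies to the AE onset date:

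- Onset month/year earlier than that of first product use: not product-emergent, unless the AE became more severe after first product use.
- Onset month/year the same or later: product-emergent, unless a known stop date precedes first product use.
- Onset date completely missing: product-emergent, with the same stop-date exception.

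The worsening clause is needed because the SAP definition counts such AEs as emergent. Without it, the new cut-point would drop a partially dated screening AE that worsened after use.

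The cost is a wording change in one table, with one added row, and the matching program step. No new data are needed. SAP section 3 allows amendments before database lock and requires later changes to be described in the clinical study report.

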12.6.4.2 Adverse Events

12.6.4.2.1 All Adverse Events

All AE tables will be presented by randomized arm.

A general summary table of AEs will be presented including:

- The number of events and the number and percentage of subjects reporting at least one AE.

- The number of events and the number and percentage of subjects reporting at least one study product –related AE, broken down by product relatedness (related to THS 2.2 / CC) and expectedness (expected for THS 2.2 / CC).
- The number of events and the number and percentage of subjects reporting at least one AE broken down by severity including each subject only once with his worst severity.
- The number of events and the number and percentage of subjects reporting at least one SAE.
- The number of events and the number and percentage of subjects reporting at least one AE leading to any action taken, broken down by action taken related to the product (product use interrupted, product use reduced, product use stopped, not applicable, none), treatment given (yes, no), study discontinuation, other action taken.
- The number of events and the number and percentage of subjects reporting at least one AE related to study procedure

Additional summary tables of AEs will be presented with a breakdown of the number of events, as well as the number and percentage of subjects reporting each AE, categorized by system organ class (SOC) and preferred term (PT) coded according to the Medical Dictionary for Regulatory Activities (MedDRA) dictionary (version 16.0):

- The number of events and the number and percentage of subjects reporting at least one AE.
- The number of events and the number and percentage of subjects with at least one AE related to product exposure and expectedness for investigational product (IP; THS 2.2 or CC).
- The number of events and the number and percentage of subjects with at least one AE leading to product discontinuation or reduction.
- The number of events and the number and percentage of subjects with at least one AE leading to study discontinuation.
- The number of events and the number and percentage of subjects with at least one AE related to study procedure.
- The number of events and the number and percentage of subjects with at least one AE by severity (mild, moderate, severe).

If a subject has more than one occurrence of the same AE, the subject will be counted only once within a PT with the worst occurrence based on the presentation (e.g., for presentation by severity = most severe, for presentation by relationship = most related). Missing information on the intensity of AE will be counted as severe.

The data will be presented in the below outputs, the TFL number refers to the TFL number in the accompanying TFL shell document:

TFL number	Title
TABLES	
15.2.6.1	Summary of Adverse Events – Safety Population
15.2.6.2.1	Summary of Adverse Events by System Organ Class and Preferred Term – Safety Population
15.2.6.2.2	Summary of Adverse Events by System Organ Class – Safety Population
15.2.6.2.3	Summary of Adverse Events by Preferred Term – Safety Population
15.2.6.3	Summary of Adverse Events by System Organ Class, Preferred Term and Relationship to Study Product Exposure for Investigational Product (THS 2.2 or CC) and Expectedness – Safety Population
15.2.6.4	Summary of Adverse Events Leading to Investigational Product (THS 2.2 or CC) Discontinuation or Reduction by System Organ Class and Preferred Term – Safety Population
15.2.6.5	Summary of Adverse Events Leading to Study Discontinuation by System Organ Class and Preferred Term – Safety Population
15.2.6.6	Summary of Adverse Events Related to Study Procedure by System Organ Class and Preferred Term – Safety Population
15.2.6.7	Summary of Adverse Events by System Organ Class, Preferred Term and Severity – Safety Population
15.2.6.8	Summary of Serious Adverse Events – Safety Population
LISTINGS	
15.3.6.1.1	Listing of Adverse Events

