12.5.4 Safety Analysis

In general, all safety data will be listed and tabulated on the safety population by product arm, using the approach described in Section 12.1.3. Safety variables collected during exposure periods will also be reported by product exposure.

Adverse event data will serve as the primary assessment of safety. Other safety variables monitored in this study include: respiratory symptoms (cough assessment VAS and Likert scales); vital signs (systolic and diastolic blood pressure, pulse rate, respiratory rate); spirometry; ECG data; clinical chemistry, hematology, concomitant medications, and urine analysis safety panel; physical examination.

Confidentiality statement: Data and information contained in this document are considered to constitute trade secrets and confidential commercial information, and the legal protections provided to such trade secrets and confidential information are hereby claimed under the applicable provisions of applicable law. No part of this document may be publicly disclosed without the written consent of Philip Morris Products S.A.

The number and percentage of subjects with AEs and SAEs will be tabulated by system organ class and preferred term. Summaries will also be presented for AEs leading to withdrawal, AEs leading to death, AEs by relatedness to product exposure, AEs by severity, and laboratory AEs. Tabulations will be performed for both the number of subjects experiencing an event and the number of events.

The number and percentage of subjects with clinical findings will be tabulated by sequence for laboratory parameters. Shift tables showing change from baseline of clinical findings will be provided for: ECGs, physical examinations, and laboratory parameters (both shifts in normal ranges and toxicity grades). Descriptive statistics will be summarized by visit and change from baseline for laboratory parameters, ECG, respiratory symptoms, and vital signs.

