9 CHANGES FROM THE PROTOCOL SPECIFIED STATISTICAL ANALYSIS

- Shift tables for safety endpoints will not be produced for this study, the relevant information will be provided in listings.
- Statistical analysis for blood COHb (%) and exhaled CO (ppm) measurements and the QSU-brief questionnaire data, MNWS questionnaire data and the MCEQ questionnaire data will be performed including interaction terms for product and time point to enable least square means to be calculated at each time point in order to explore the pattern of the THS 2.2 effect over time. The main comparison between products will be the comparison over all time points.
- The second exploratory objective (“To evaluate in smokers switching from CC to THS 2.2, smokers continuing smoking CC and smokers switching from CC to SA the relationship between:

- Primary and secondary BoExp and NEQ
- Selected risk markers and, primary and secondary BoExp, and NEQ

will now only investigate:

- 1) The relationship between primary and secondary BoExp and NEQ, which will be reported in a separate report.
- 2) The relationship between risk markers and NEQ, which will be reported in the CSR.

- The term “adjusted to creatinine” has been replaced by “adjusted for creatinine” in all relevant endpoints and analyses.

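### AE tables put events from before the assigned regimen into randomized-arm columns with no split by period, and the SAP gives two conflicting grouping rules for those tables

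*SAP*

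**What the plan says.** **Window.** SAP 12.6.4.1: "An exposure emergent AE is defined as an AE that occurs after first product use". It also includes earlier events that worsen after first use, and it gives no end point. The SAP does not say in words what first product use is. Protocol 8.5 identifies it as the THS 2.2 product test on the Admission Day (Day -2). SAP 12.6.4.1 agrees with this by implication: "AEs reported from subjects that have a first product use, but were not randomized will be summarized in a separate group", a group that can exist only if first use precedes randomization.

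**Timing.** SAP 6.1: "Subjects are enrolled on Day -2, and then randomized on Day 0". The exposure period runs from Day 1 06:30 to Day 5 23:00. AEs are collected until the end of study (Protocol 8.2.1), and in follow-up only by spontaneous report (Protocol 8.2.4).

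**Columns.** SAP 12.6.4.2.1: "All AE tables will be presented by randomized arm". In the general summary, product-related AEs are "broken down by product relatedness (related to THS 2.2 / CC" and by expectedness.

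**The other grouping rule.** SAP 10.3 and 12.1.3 present the Safety Population by actual exposure, and SAP 12.6.4.2.3 does the same for AEs leading to withdrawal.

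**Protocol.** Section 12.5.4 asks for tabulation by product arm, makes AE data the primary assessment of safety, and adds: "Safety variables collected during exposure periods will also be reported by product exposure".

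**The concern.** A column headed SA or CC will be read as what happened on that regimen. Under these rules it also holds events from a period when every subject had tried THS 2.2 and was smoking their own cigarettes. Someone comparing THS 2.2 with SA cannot tell from the table which events arose on the assigned regimen, which preceded it, and which came after discharge.

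The grouping conflict is a separate matter. Two programmers following the same SAP could build different AE tables, and both could point to a sentence that supports them.

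**Working it through.** **1. Calendar.** Inclusive counts with a Day 0 reproduce the protocol's own durations: Day -30 to Day 13 = 44 days, Day -3 to Day 13 = 17 days, and Day -2 to Day 6 = 9 days of confinement. The summarized AE window, Day -2 to Day 13, is 16 days: 3 before exposure, 5 in the exposure period and 8 after it.

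**2. Actively monitored hours.** Assumed: product test at 16:00 on Day -2 (Protocol 4.4 puts the start of confinement in the afternoon) and discharge at 10:00 on Day 6.
- Before the regimen: Day -2 16:00 to Day 1 06:30 = 8 + 24 + 24 + 6.5 = 62.5 h
- Regimen: Day 1 06:30 to Day 5 23:00 = 112.5 h
- Day 5 23:00 to discharge = 11 h, so Day 1 06:30 to discharge = 123.5 h
- Total = 62.5 + 123.5 = 186 h; share before the regimen = 62.5/186 = 33.6%
- Range: test 12:00 and discharge 07:00 give 66.5/187 = 35.6%; test 22:00 and discharge 24:00 give 56.5/194 = 29.1%

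Randomization can take place at any time on Day 0, so 32 to 56 of the 186 h (17-30%) precede randomization itself.

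**3. What each column receives before Day 1 06:30.**
- SA: AEs from test sticks and from own cigarettes, neither of which is the regimen.
- THS 2.2: AEs from own cigarettes, and AEs from test sticks that cannot be told apart from AEs on assigned sticks.
- CC: mainly test-stick AEs are out of place, because own cigarettes are also the assigned product.

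The SAP sets such events apart only for subjects who were never randomized.

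**4. Is a split planned?** None of the AE table titles in SAP 12.6.4.2.1 to 12.6.4.2.3, 13.2 or 13.3 is limited to a period or divided by one. SAP 13.4 says that all outputs are listed in the SAP. Where a time split is meant, the SAP names it: cough has a table by study day (SAP 12.6.4.5.6).

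**5. Grouping rules side by side.** Table 15.2.6.5 (AEs leading to study discontinuation) is listed in 12.6.4.2.1 under the randomized-arm rule and in 12.6.4.2.3 under the actual-exposure rule. By SAP 10.3, membership of the Safety Population requires exposure to THS 2.2, so taken literally actual exposure does not separate the arms. It also groups subjects and sets no time window, so adopting it would not resolve steps 3 and 4.

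**6. Partial dates.** An AE with a partial date is product-emergent under this condition: "If month/year is the same as, or later than the month and/or year of Screening". The anchor is Screening, which can be weeks before first product use, so an event that began before any product use can be classed as emergent.

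**7. Size, by illustration (all rates assumed).** Take 20% of CC subjects with an AE in the 186 h, a constant background rate of -ln(0.8)/186 = 0.0012 per h, and a true rate ratio of 2 during regimen hours. The comparator is a table from Day 1 06:30 to discharge.
- The expected excess is 0.0012 x 112.5 = 0.135 events per subject in every window, so pooling does not bias it.
- Percent of subjects with an AE, 1 - exp(-mean events): 13.8 vs 24.7 (gap 10.9 points) from Day 1 06:30 to discharge; 20.0 vs 30.1 (gap 10.1) from the product test to discharge; a gap of 8.3 with follow-up at equal ascertainment.
- Standard error of the difference in events per subject (80 vs 40 subjects): 0.085, 0.100 and 0.133, that is +18% and +56%. The figures with follow-up are upper bounds on the effect, because follow-up reporting is passive.

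**The case against.** The defence has several good points.

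- Tabulating AEs by arm is what Protocol 12.5.4 asks for, so the randomized-arm rule is not in itself a departure. This stands.
- A reader might infer that the SAP silently drops an exposure-period AE table that the protocol requires, and that section 9 should have said so, since it does record that "Shift tables for safety endpoints will not be produced for this study". The documents do not establish this. Protocol 12.5.4 speaks of reporting by product exposure. It names no table and no time window, and it can be read as a grouping rule. An exposure-period display is one reading of it.
- A reader might also infer that follow-up AEs do not belong in arm columns. They do: AEs are collected to end of study, and late events should stay visible. The difficulty is only that they cannot be told apart.
- Timing can be recovered. Onset dates and times are recorded, and all AEs are listed. A THS-related AE under SA or CC will normally point back to the Day -2 test. That helps for those two columns. It does not help within the THS 2.2 column, or for AEs judged unrelated.
- The separate TFL shells (SAP 3) might split columns by period. SAP 13.4 makes extra tables unlikely but does not settle the layout within a table.
- On grouping, the sentence in 12.6.4.2.1 is the specific rule, and SAP Table 17 gives THS 2.2, CC and SA as labels. With products dispensed one at a time in confinement, the two groupings would seldom differ. The contradiction with 12.6.4.2.3 remains.

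**Conclusion.** The point holds as a matter of attribution and drafting. Followed exactly, the SAP places AEs from before the assigned regimen in the arm columns, and about one third of actively monitored time (29-36% under the assumed test and discharge times) lies there. It also states two grouping rules for AE tables and leaves one of them undefined.

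The consequence is limited to descriptive reading. No AE test is planned. With the same background rate in each arm, the expected difference in event counts is not biased, so a reader should not infer that the safety comparison is invalid. In the illustration, pooling the hours before the regimen narrows the gap in percent of subjects by 0.8 points (10.9 to 10.1). The documents give no AE rate, so that figure rests wholly on assumed values. The grouping conflict probably changes few numbers. The change is still worth making, because AE data are the primary assessment of safety and the cost is small.

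**What to change.** 1. In SAP 12.6.4.1, state that first product use is the Day -2 product test and derive a period flag from AE onset date and time: product test to Day 1 06:29; Day 1 06:30 to discharge, noting that the hours after Day 5 23:00 are off product in the THS 2.2 and CC arms; safety follow-up. Anchor the partial-date rule on first product use instead of Screening, and say how a partial onset date is assigned to a period.
2. Add Day 1 06:30-to-discharge versions of Tables 15.2.6.1 and 15.2.6.2.1 by THS 2.2, CC and SA. Keep the all-emergent tables. This would also satisfy the exposure-period reading of Protocol 12.5.4.
3. Choose one grouping rule for AE tables, define actual exposure so that the product test alone does not determine it, and align SAP 10.3, 12.1.3, 12.6.4.2.1 and 12.6.4.2.3.

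Cost: SAP wording, one derived variable from onset times already collected (Protocol 8.2.1), and two more descriptive tables. No new data.
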